12.2 Demographic and Baseline Characteristics

For all demographic and baseline characteristics assessments presented below the baseline is defined as the last available assessment collected before the first administration of study drug. Further details are given in [Section 10.2](#).

Demographic and baseline characteristics will be summarized by treatment sequence and overall using appropriate summary statistics as described in [Section 12.0](#) in the FAS and the Randomized Analysis Set if different from FAS.

If deemed appropriate (i.e., more than 20 % of the randomized patients experiencing at least one major protocol deviation, as defined in Appendix 1 Classification of Protocol Deviations), demographic and selected baseline characteristics will also be summarized using the PP Analysis Set. and may also be summarized on the Study Completer Analysis Set.

All summaries for continuous parameters will be based on non-missing observation. For categorical variables, the percentage will be based on the total number of patients, within the studied dataset, overall and per treatment sequence (i.e., each denominator includes the number of patients with missing/unknown value for this parameter).

Demographic, baseline characteristics, and disease history data will also be listed with a flag identifying those belonging to the FAS, the PP Analysis Set, the Study Completer Analysis Set, and the Safety Analysis Set.

All baseline safety and efficacy parameters (apart those presented below) are presented along with summary statistics in the safety and the efficacy sections, respectively ([Section 12.7](#) and [Section 12.5](#)).

12.2.1 Demographics Characteristics

As defined in [Section 10.10](#), the following demographic and baseline characteristics will be summarized:

- Age (years),

- Age groups (≤ 18, > 18 to ≤ 45; ≥ 46 to ≤ 65; > 65 years old),
- Sex (Male, Female),
- Race (White, Black or African American, Asian, American India or Alaska Native, Native Hawaiian or Other Pacific Islander, other) (per legal data protection law),
- Country (Spain, UK, Poland, Czech Republic, USA)*,
- Region (USA Region, Non-USA Region)

* This includes any additional country with sites where patients will be enrolled and exposed to at least one dose of IMP.

12.2.2 Baseline Physical Examination

As defined in [Section 10.11](#), the following baseline physical examination will be summarized.

- Baseline height (cm),
- Baseline weight (kg),
- Baseline BMI (kg/m²),
- Baseline BMI category (< 18.5 as underweight; ≥ 18.5 and < 25.0 as normal or Healthy Weight; ≥ 25.0 and < 30.0 as overweight; ≥ 30 as obese),

12.2.3 Baseline Vital Signs

- Baseline Supine Systolic blood pressure (SBP) (mmHg),
- Baseline Orthostatic SBP (mmHg)
Orthostatic SBP being defined as supine SBP- Standing SBP,
- Baseline Orthostatic SBP ≥ - 20 mm Hg,
- Baseline Supine Diastolic blood pressure (DBP) (mmHg),
- Baseline Orthostatic DBP (mmHg)
Orthostatic DBP being defined as supine DBP- Standing DBP,
- Baseline Orthostatic DBP ≥ - 10 mm Hg,
- Baseline Supine Heart Rate (HR) (Beats/min),
- Baseline Orthostatic HR (Beats/min)
Orthostatic HR being defined as supine HR- Standing HR,
- Proportion of patients who meet criteria for orthostatic hypotension.
defined as either drop in SBP of 20 mmHg or greater or drop in DBP of 10 mmHg or greater.

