## **13.4 General Considerations**

Unless stated otherwise, continuous variables will be summarized showing the number of non-missing values (n), mean, SD, median, minimum, and maximum. Categorical variables will be summarized showing the number and percentage of patients falling in each category.

For patient electronic diary-based endpoints, baseline is defined as the average of the last 7 days of electronic diary entries prior to randomization (Visit 2).

For clinic-based endpoints, baseline is defined as the last record or measure collected prior to the first dose of IMP in each treatment period.

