6.2 Changes from Protocol

Table 6.2-1 Change from Protocol

Section of SAP Affected	Type of Change	Rational
Section 9.6.2.3,Section 11.0 and Section 12.5	Change to the definition of the Full Analysis Set (FAS) that is detailed in Protocol Section 13.3	
The FAS includes all patients who have taken a dose of investigational medicinal product (IMP). Per our specified estimand, patients should continue Period 1 despite stopping IMP. Hence, if a patient withdraws from the study, they should be handled as a missing data problem and will be imputed per this analysis plan.
 
Since IMP was taken, withdrawal may have been due to IMP and hence it may be important to include this patient in the analysis.

Section 7.3,Section 9.1,Section 10.15 and Section 12.5	Addition of an exploratory objective/ endpoint, the Lower Limb Muscle Tone-10 to those presented in Protocol Section 2 and Section 13.6.2	Since hip flexors and hip adductors are being collected the Lower Limb Muscle Tone-10 was added as exploratory endpoints

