10.2 Baseline

For patient electronic diary-based endpoints (NRS-spasticity and spasm count, respectively), baseline is defined as the weekly average of daily electronic diary entries over the last 7 days prior to randomization (Visit 2, Period1 Day 1H0).

In case of missing assessments within the 7 days preceding Period1 Day1 H0

For 11-point NRS spasticity scale, the weekly average will be set to missing if scores are missing for 4 days in total or for 3 consecutive days within the 7-days period.

For daily spasm count, the weekly average will be derived as detailed in [Section 10.19](#)) and will be set to missing if spasm count is not collected during 4 days out of 7 or for 3 consecutive days during the last 7 days preceding Day 1H0.

For clinic-efficacy based endpoints, baseline is defined as the last record or measure collected prior to the first dose of IMP in each treatment period.

However, if deemed necessary the baseline will be defined for each period as described in [Section 10.1.2](#) as:

the reference day for Period 1,

the reference day for Period 2,

For clinic-safety based endpoints, baseline is defined as the last record or measure collected prior to the first dose of IMP or if deemed necessary as the reference day as described in [Section 10.1.2](#).

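### SAP 12.2.3 gives two orthostatic blood-pressure rows the wrong sign; the per-period vital-sign baseline and the Visit 1 posture also need to be settled

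*SAP*

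**What the plan says.** **Orthostatic rows.** SAP 12.2.3 fixes the sign convention: "Orthostatic SBP being defined as supine SBP- Standing SBP", with diastolic pressure treated the same way. It then lists "Baseline Orthostatic SBP ≥ - 20 mm Hg" and "Baseline Orthostatic DBP ≥ - 10 mm Hg". The last item in the list, the proportion with orthostatic hypotension, is "defined as either drop in SBP of 20 mmHg or greater or drop in DBP of 10 mmHg or greater". For categorical baseline variables SAP 12.2 adds that "each denominator includes the number of patients with missing/unknown value for this parameter".

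**Baseline for change.** Protocol 13.4 says: "For clinic-based endpoints, baseline is defined as the last record or measure collected prior to the first dose of IMP in each treatment period". SAP 10.2 keeps the per-period wording for clinic efficacy endpoints, but for safety it reads: "For clinic-safety based endpoints, baseline is defined as the last record or measure collected prior to the first dose of IMP or if deemed necessary", after which it points to the reference day of SAP 10.1.2. That section has separate reference days for Period 1 and Period 2. SAP 12.7.4 summarises on-treatment change in vital signs at Day 1 H3, Day 15 and Day 21 by treatment arm without naming the baseline. The laboratory and ECG sections (12.7.3 and 12.7.5.2) name Screening. SAP Table 6.2-1 declares "Change to the definition of the Full Analysis Set (FAS) that is detailed in Protocol Section 13.3" and the added LLMT-10 endpoint, but nothing on the safety baseline.

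**Posture.** Protocol 9.2.10 has Visit 1 vital signs taken supine and then, in ambulatory patients, standing; all later readings are sitting. Exclusion criterion 6.2.12 applies sitting blood-pressure limits at Visit 1 or Visit 2. SAP 12.7.4 counts the screening visit among the sitting readings and runs the follow-up change from Screening.

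**The concern.** A programmer who codes the two orthostatic rows as printed will produce counts that look like postural-drop counts but contain almost every patient measured. A reader of the baseline table could take them for a very high frequency of postural drop.

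The other two points concern how vital-sign change is computed, which is a listed secondary safety endpoint. If two programmers can defend different baselines, Period 2 changes and the Appendix 6 abnormality flags can differ, because Appendix 6 requires both a value criterion and a change criterion. If the Screening value is supine and the follow-up value is sitting, the supine–sitting difference enters the follow-up change one for one, in both sequences.

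The SAP addendum, written after the study was stopped, lists vital signs among the safety items to be reported as set out in the SAP, so the wording of 12.7.4 still matters. The addendum does not mention the 12.2.3 baseline table.

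**Working it through.** The plan gives no figure to reproduce here. The check applies the SAP's own definition and then compares passages.

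**1. Orthostatic rows.** Let X = supine − standing (SAP 12.2.3). The readings below are chosen for illustration, with supine SBP 130 and supine DBP 80.

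| Standing SBP | X | X ≥ −20 (as written) | X ≥ 20 | Standing DBP | X | X ≥ −10 (as written) | X ≥ 10 |
|---|---|---|---|---|---|---|---|
| 105 | 25 | yes | yes | 68 | 12 | yes | yes |
| 110 | 20 | yes | yes | 70 | 10 | yes | yes |
| 130 | 0 | yes | no | 80 | 0 | yes | no |
| 145 | −15 | yes | no | 88 | −8 | yes | no |
| 150 | −20 | yes | no | 90 | −10 | yes | no |
| 151 | −21 | no | no | 91 | −11 | no | no |

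As written, each row counts 5 of 6. With a positive cut-off each counts 2 of 6, exactly those with a drop under the hypotension line.

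Reversing the subtraction does not rescue the rows. With standing − supine ≥ −20, a patient going from 120 to 120 is counted (0), while one going from 120 to 95 (−25, a 25 mmHg drop) is missed.

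The documents give no distribution for X. If X is taken as normal, with all means and SDs assumed:

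- SBP, mean 0 to 10, SD 8 to 15: as written 91–100%; with ≥ 20, 1–25%.
- SBP with drops above 20 removed, as criterion 6.2.12 requires: as written 90–100%; with ≥ 20, 0–3%, because only a drop of exactly 20 can remain.
- DBP, mean −5 to 10, SD 6 to 10: as written 69–100%; with ≥ 10, 1–50%.

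These are shares of patients with a standing reading. Table percentages will be lower, because non-ambulatory patients have none and SAP 12.2 keeps them in the denominator.

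**2. Baseline for on-treatment change.** Read literally, the SAP 10.2 default is the last value before the first IMP dose of the trial, which is Visit 2 pre-dose. Period 2 readings on Days 31, 45 and 51 then lie 31 − 1 = 30, 45 − 1 = 44 and 51 − 1 = 50 days from baseline. From Visit 6 pre-dose they lie 0, 14 and 20 days away.

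Worked flag (Appendix 6: SBP below 90 and a fall of at least 20): with 112 on Day 1, 105 on Day 31 pre-dose and 88 on Day 45, the fall is 112 − 88 = 24 (flagged) or 105 − 88 = 17 (not flagged).

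To gauge frequency, three independent readings around a patient mean were simulated with no time or treatment effect (4,000,000 patients per setting). All means and SDs are assumptions.

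- SBP: mean 115 or 125, between-patient SD 10 or 14, within-patient SD 6 or 10, Day 1 value limited to 90–150 as in 6.2.12. Period 2 readings below 90: 0.11–4.86%. Flags differ in 9.7–39.7% of those, which is 0.02–1.75% of all Period 2 SBP readings.
- Pulse: mean 70 or 78, between-patient SD 8 or 11, within-patient SD 5 or 8. Readings below 50: 0.15–7.05%. Flags differ in 23.4–37.1% of those, or 0.05–2.56% of all.

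**3. Posture.** The passages side by side:

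- Protocol 9.2.10: Visit 1 supine then standing; sitting at every later time point.
- SAP 12.2.3: supine and standing baselines, which under 9.2.10 only Visit 1 can supply.
- Protocol 6.2.12: sitting limits at Visit 1 or Visit 2. It also uses a postural drop at either visit, although 9.2.10 provides only sitting readings at Visit 2.
- SAP 12.7.4: sitting values, screening included.

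If only the 9.2.10 readings exist at Visit 1, the follow-up change compares supine with sitting. If a sitting reading was also recorded, it need not. The documents give no figure for the supine–sitting difference.

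**The case against.** **On the rows.** In the text available for review, comparison signs are lost in places (for example the spray categories in SAP 10.8.2 and the duration categories in 10.21.4), so the printed signs should be checked against the PDF. That is a caveat and no more: those are missing signs, whereas here a minus sign appears in both rows. It is also fair that the hypotension line already reports the meaningful result, and that criterion 6.2.12 leaves the corrected systolic row nearly empty. A reader might infer that baseline orthostatic hypotension itself will be misreported. The documents do not support that, since that line is worded correctly.

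**On the baseline.** A reader might infer that the SAP states no baseline for vital signs. It does state one, in 10.2. Several passages also point to a period baseline. SAP Table 9.1-1 lists these changes by treatment period. SAP 10.1.2 derives an analysis day from each period's own reference day for analyses by arm. Table 10.1-2, as far as its layout can be read, gives a Visit 6 Day 1 H0 window before Period 2 dosing. Weight (12.7.5.1) lists Period 2 Day 1 H0 as a change timepoint, while vital signs do not. The general wording of 10.2 may simply reflect that laboratory and ECG are scheduled only at Visits 1, 5 and 9. All this stands and makes the literal Day 1 reading the less likely one. What remains is that 12.7.4 does not say so, the option in 10.2 has no trigger, and the difference from protocol 13.4 is undeclared.

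**On posture.** Protocol 9.2.10 does not forbid a sitting reading at Visit 1 and may only be incomplete. Naming Screening for the follow-up change may be deliberate, as weight uses it too. A reader might infer that the follow-up change certainly mixes postures. The documents do not show which Visit 1 value was recorded, so that cannot be claimed.

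**Conclusion.** **Orthostatic rows: wrong as written, high confidence.** The conclusion follows from the definition in the same section and fails under either sign convention. It affects two descriptive baseline rows. The percentages above are illustrations under assumed distributions; the 5 of 6 against 2 of 6 comparison needs only the definition.

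**Baseline: stated but left open, lower confidence, small effect.** A period baseline is the likelier intent. Only if 10.2 is read literally do Period 2 changes and flags run from Day 1. Even then, under the assumed means and SDs, the choice alters the flag for at most about 1.75% of Period 2 systolic readings and 2.56% of pulse readings.

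**Posture: conditional.** The passages conflict. Whether the follow-up change is affected depends on whether a sitting Screening value was recorded, and its size cannot be given from the documents.

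Overall minor. No hypothesis test, alpha allocation or primary result changes.

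**What to change.** 1. **SAP 12.2.3:** change the two rows to ≥ 20 mmHg (SBP) and ≥ 10 mmHg (DBP), matching the hypotension line.
2. **SAP 10.2 and 12.7.4, vital signs only:** state that baseline for on-treatment change and for the Appendix 6 change criteria is the last pre-dose value of each treatment period (Visit 2, Visit 6), and remove the open reference-day option for these variables.
3. **SAP Table 6.2-1:** declare that laboratory and ECG use Screening, which differs from protocol 13.4. They have no scheduled Visit 6 pre-dose value.
4. **Posture:** reconcile protocol 9.2.10, protocol 6.2.12, SAP 12.2.3 and SAP 12.7.4 on the Visit 1 readings. If no sitting Screening value was recorded, use the Visit 2 pre-dose sitting value as baseline for the follow-up summary. That choice is like-for-like on either reading of Visit 1. A recorded sitting Screening value would also serve.

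The cost is a few short SAP edits and a reconciliation note. No new data are needed, since pre-dose vital signs at Visits 2 and 6 are already scheduled. No eligibility change is asked for, as enrolment has been halted.

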12.2.4 Medical History

Previous and current medical conditions (medical history) will be coded using the Medical Dictionary for Regulatory Activities (MedDRA) version 24.0 or higher and will be summarized by system organ class (SOC) and preferred term (PT) per treatment sequence and overall in the FAS.

12.2.5 Disease Characteristics

The following disease characteristics will be summarized.

Multiple sclerosis diagnosis

As defined in [Section 10.12](#):

MS subtype (primary progressive, secondary progressive, relapsing-remitting),
Time since diagnosis of MS (years),

Age at diagnosis of MS (years),
Time since onset of spasticity due to MS (expressed in months or years as appropriate),
Age at onset of spasticity due to MS (years),
Time between MS diagnosis and onset of spasticity due to MS (months or years as appropriate),
○ also presenting the number and percentage of patients experiencing spasticity before MS diagnosis,
Time between MS diagnosis and onset of spasticity due to MS (years),
Number of relapses in the past 12 months,
Time since last relapse (months or years as appropriate),

Current MS medications

As defined in [Section 12.3.2](#), the following summaries relative to current MS medications will be provided:

- At least 1 MS medication
 - At least 1 antispasticity medication
 - Baclofen,
 - Tizanidine,
 - Dantrolene,
 - Benzodiazepine,
 - Muscle relaxants,
 - Botulinum toxin,
 - Gabapentin,
 - Pregabalin,
 - Other.
 - Number of antispasticity medications used
 - 0,
 - 1,
 - 2,
 - ≥ 3 .
 - At least 1 MS disease modifying drug (DMD),
 - At least 1 medication to treat other MS Symptoms,
 - Dalfampridine,
 - Fampridine.

Current MS medications are those taken at time of randomization/1st IMP dosing as described in [Section 12.3.2](#)). They will be determined based on information retrieved from eCRF concomitant medication form; further determination criteria being given in [Appendix 10](#) Medications used in MS and determination criteria

Prior use of cannabis or cannabinoid

At Screening (Visit 1), any intermittent or regular previous use of cannabis or cannabinoid products for medical or recreational purposes will be recorded.

- Prior use of cannabis or cannabinoid will be summarized for the following
- Prior use of cannabis or cannabinoid
 - Medicinal use,

- Recreational use.

12.2.6 Baseline Efficacy Endpoints

The following endpoints derived from MAS transformed scores (as defined in [Section 10.16](#)) will be summarized:

- Baseline Lower Limb Muscle Tone-6,
- Baseline Lower Limb Muscle Tone-4,
- Baseline Lower Limb Muscle Tone-10,

The following other endpoint will be summarized:

- Baseline 7-day average NRS Spasticity Score

12.2.7 Baseline Safety Endpoints

The following baseline safety endpoints linked to renal function and C-SSRS will be summarized

- Renal function (as defined in [Section 10.13](#))
 - Baseline eGFR (ml/min/1.73m²),
 - Baseline eGFR category (ml/min/1.73m²): ≥ 90 as normal, ≥ 60 and < 90 as mild reduction, ≥ 30 and < 60 as moderate reduction, ≥ 15 and < 30 as severe reduction, < 15 as end-stage kidney failure.
- C-SSRS (as defined in [Section 10.23](#))
 - Baseline Suicidal Ideation Score,
 - Baseline Suicidal Behavior.

12.3 Treatments

12.3.1 Extent of Exposure

Exposure to study drug, IMP dosing, treatment compliance and drug accountability will be presented using the Safety Analysis set.

12.3.1.1 Duration of Therapy

The extent of exposure will be for each study drug (e.g., Nabiximols or placebo) the total number of days of administration of IMP, ignoring temporary drug discontinuation, within the designated treatment period.

The duration of exposure (as defined in [Section 10.7](#)) will be summarized descriptively as quantitative variable (number, mean, SD, median, Q1, Q3, minimum and maximum) but also presenting the total number of days and the mean number of days (expressed in patient-week) as defined in [Section 10.7](#).

The number and percentage of patients with an extent of exposure within a predefined study day range will also be presented for each of the following categories and the cumulative distribution according to these categories:

- Day 1 to 7,
- Day 8 to 14,
- Day 15 to 21,
- Day 21.

Extend to exposure will also be summarized per treatment arm by subgroups of interest as presented in [Table 12.1-1](#).

12.3.1.2 IMP Dosing

Patients are expected to record, daily, the number of morning and evening spray(s) they have taken in their eDiary. This information will be integrated in the eCRF.

At Day 15 of each treatment period (at the end of the titration phase), the daily number of sprays to be taken by each patient defined as the optimized dose will be reported in the eCRF "Dose adjustment" form.

Whenever a patient has taken an amended dose, this will also be reported in the eCRF "Dose adjustment" form along with start and stop date of each amended dose and the reason why the optimized dose was amended (e.g., adverse event, insufficient therapeutic effect, other).

During the Titration Phase (up to Day 14)

The number of sprays taken will be summarized by day as quantitative variable (n, mean, SD, median, Q1, Q3, min and max) but also presenting per day, the number of sprays administered as a categorical variable.

Additionally,

- the rate of missing diary day information (%),
- the patient percentage of imputed diary days (%),
- the patient total number of daily sprays,
- the patient mean number of sprays,
- the patient mode number of daily sprays,
- the patient median number of daily sprays
- the rate of "0" total daily sprays (%),
- the rate of ">12" total daily sprays (%),

as defined in [Section 10.8.2](#) and [Section 10.9](#), will be summarized per treatment arm as quantitative variable (n, mean, SD, median, Q1, Q3, min and max).

During the Maintenance Phase (Day 15 to Day 21)

As defined in [Section 10.8.2](#),

- the patient total number of sprays,
- the patient mean number of daily sprays,
- the patient mode number of daily sprays,
- the patient median number of daily sprays,

Combined: During the Titration Phase (up to Day 14) + Maintenance Phase (Day 15 to Day 21)

- the rate of "0" total daily sprays (%),
- the patient maximal number of daily sprays

will be summarized as quantitative variable (n, mean, SD, median, Q1, Q3, min and max).

In addition, the patient mean number of daily sprays used by patient will be categorized as ≤ 6 sprays; ≤ 12 sprays and >12 sprays and summarized.

As defined in [Section 10.9](#),

- the rate of missing diary day information (%),

- the patient percentage of imputed diary days (%),
- the rate of “0” total daily sprays (%),
- the rate of >12 total daily sprays (%),

will be summarized per treatment arm as quantitative variable (n, mean, SD, Median, Q1, Q3 min and max). These four parameters are also part of compliance assessment (as presented in [Section 12.3.1.3](#)).

Graphical Representations

The mean (\pm SD) number of sprays will also be presented by day using a line plot by treatment arm.

The patient mean number of daily sprays during the titration phase, during the maintenance phase and overall will also be presented by treatment arm using a cumulative distribution function.

